#### 4.6.2. Secondary Efficacy Analyses

Analyses for the secondary endpoints will be conducted using the FAS and PP populations. Where applicable, baseline is defined as the last non-missing pre-treatment assessment prior to initiation of study treatment.

All secondary endpoints that reflect a dichotomous response will be analyzed in the same manner as the primary efficacy endpoint. These secondary endpoints include

- Proportion of subjects with endoscopic response at Week 12 (Day 84) (defined as an endoscopic subscore of 0 or 1)
- Proportion of subjects with clinical response at Week 12 (Day 84) (defined as at least 1 point and 30% reduction from baseline in rectal bleeding and stool frequency subscores)
- Proportion of subjects developing neutralizing antidrug antibodies (ADA)
  - Methods for detection of ADA in clinical samples are presented in Section 7.8 of the protocol
- Proportion of subjects with endoscopic remission at Week 12 (defined as an endoscopic subscore of 0)

Hypothesis testing for all continuous secondary endpoints will be conducted using repeated measures mixed analysis of covariance model adjusted for treatment, time point, treatment-by-time point interaction, stratification factor (TNF-alpha prior use) and baseline values. For subjects who withdraw prematurely, the last observation will be carried forward. These analyses will be based on the Stage 1 and Stage 2 combined data for exploratory purposes. Pairwise comparisons of active drug versus placebo for the change from baseline endpoints will be conducted and p-values derived as described in the analysis of the primary efficacy endpoint. In addition, a summary of observed values and change from baseline values will be presented for each endpoint. Graphical summaries by treatment group of mean change from baseline over time up to Week 12 will also be presented.

Continuous secondary endpoints include

- Mean change in complete Mayo Score (including all four subscores) from baseline to Week 12
- Mean change in Partial Mayo Score (excluding endoscopy subscore) from baseline to Weeks 2, 4, 6, 8, 10, 12, and 16 (Days 14, 28, 42, 56, 70, 84, and 112)
- Mean change in endoscopy subscore from baseline to Week 12 (Day 84)
- Mean change in rectal bleeding and stool frequency subscores from baseline to Weeks 2, 4, 6, 8, 10, 12, and 16 (Days 14, 28, 42, 56, 70, 84, and 112)
- Mean change in fecal calprotectin levels from baseline to Weeks 6 and 12
- Mean change in IBDQ score from baseline to week 12

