### 4.2. General Statistical Methods and Data Handling

#### 4.2.1. General Methods

All output will be incorporated into Microsoft Excel or Word files, sorted and labeled according to The International Council for Harmonisation of Technical Requirements for Pharmaceuticals for Human Use (ICH) recommendations, and formatted to the appropriate page size(s).

Tabulations will be produced for appropriate demographic, baseline, efficacy, pharmacokinetic, pharmacodynamic and safety parameters. For categorical variables, summary tabulations of the number and percentage within each category (with a category for missing data) of the parameter will be presented. For continuous variables, the mean, median, standard deviation, minimum and maximum values will be presented.

Formal statistical hypothesis testing will be performed on the primary efficacy endpoint with all tests conducted at the 1-sided, 0.025 level of significance. Summary statistics will be presented, as well as confidence intervals on selected parameters, as described in the sections below.

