#### 4.2.5. Multiple Comparisons/Multiplicity

Multiplicity will be addressed via a closed testing procedure with combined p-values computed for each of the two stages of the trial (interim analysis and post-interim analysis). Each stage p-value will be adjusted as appropriate by a closed testing multiple comparison approach that controls the overall type 1 error at alpha equal to 0.025, one-sided. Further details will be provided in Section 4.6.

Testing of secondary endpoints will only be performed if the primary efficacy null hypothesis is rejected. A hierarchical testing procedure will be used for the multiple secondary endpoints at the 0.025 (one-sided) alpha level. The first ten secondary endpoints will be tested in the order that they are presented in Section 2.5.1. For secondary endpoints compared at multiple time points, only the comparison at Week 12 will be used for hierarchical testing purposes.

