#### 4.2.8. Missing, Unused, and Spurious Data

All data recorded on the CRF will be included in data listings that will accompany the clinical study report.

For the primary efficacy endpoint and other success/failure secondary endpoints, subjects who discontinue prior to Week 12 will be considered treatment failures, a worst-case scenario.

These endpoints include

- Clinical Remission (primary endpoint)
- Clinical Response
- Endoscopic Response
- Endoscopic Remission

A single sensitivity analysis on each of these endpoints will utilize the per protocol population (complete-case) in order to examine the robustness of the results.

For all continuous secondary endpoints, data will be analyzed using a mixed model repeated measures approach described in Section 4.6.2. The MMRM method assume that missing data arose from a missing at random (MAR) mechanism, i.e. the missing data is independent of unobserved data given the non-missing data. The MAR assumption is reasonable in clinical trials as the observed data explain much of the missingness in many scenarios, particularly in well controlled studies such as clinical trials, in which an extensive effort is made to observe all the outcomes and the factors that influence them. In MMRM, the information from the observed data is used via the within-patient correlation structure to provide information about unobserved data. The data from all visits are simultaneously analyzed using restricted maximum likelihood methods and no explicit imputation for missing values is performed. This method will be used in the testing of the secondary endpoints.

In addition, sensitivity analyses may be performed on complete datasets where missing data is imputed using the following methodology:

- LOCF (last observation carried forward)
- WOCF (missing data imputed using the worst observation observed prior to that time point)
- Per Protocol population (complete-case scenario- no imputation required)
- Multiple Imputation

For multiple imputation, two approaches may be used. In the first approach, for missing response data at various time points, the following steps are taken:

- Draw a random sample from the normal distribution with a mean and variance calculated from the non-missing responses at that time point
- Repeat this process five times to form five imputed complete datasets
- Fit the MMRM model to each imputed dataset to estimate the treatment effect on the response variable and the variance

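### SAP 4.2.8 tests the continuous secondary endpoints by MMRM without imputation, while SAP 4.6.2 carries the last observation forward in the same model

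*SAP*

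**What the plan says.** **Missing data.** SAP 4.2.8 analyses all continuous secondary endpoints by MMRM under a missing-at-random assumption and refers to Section 4.6.2 for the model. It then says that "no explicit imputation for missing values is performed. This method will be used in the testing of the secondary endpoints". LOCF comes next, as the first entry in a list introduced by "In addition, sensitivity analyses may be performed on complete datasets where missing data is imputed using the following methodology".

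SAP 4.6.2 describes that model in a paragraph on hypothesis testing for all continuous secondary endpoints, and includes: "For subjects who withdraw prematurely, the last observation will be carried forward". The sentence is not labelled a sensitivity analysis. It repeats Protocol 7.4 and the protocol synopsis.

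**Status of the tests.**
- SAP 4.2.1: "Formal statistical hypothesis testing will be performed on the primary efficacy endpoint with all tests conducted at the 1-sided, 0.025 level of significance".
- SAP 4.2.5: "A hierarchical testing procedure will be used for the multiple secondary endpoints at the 0.025 (one-sided) alpha level". Testing starts only if the primary null is rejected, follows the order of SAP 2.5.1, and uses Week 12 where an endpoint has several time points.
- SAP 4.6.2: "These analyses will be based on the Stage 1 and Stage 2 combined data for exploratory purposes". The next sentence has active-versus-placebo comparisons with "p-values derived as described in the analysis of the primary efficacy endpoint".

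**Changes from the protocol.** SAP Section 5 declares none. Protocol 7.4 contains neither the secondary hierarchy nor a model without imputation.

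**The concern.** Two programmers could each follow the SAP and obtain different Week 12 estimates and p-values for the same endpoint. In a fixed sequence, that can also move the point at which testing stops. If the conflict is still open when treatment codes are released, the choice could be influenced by the results.

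The status wording adds to this. The same analyses are placed in a gated one-sided 0.025 hierarchy, given an exploratory label on pooled data, and assigned p-values derived by the primary method, which combines the two stages rather than pooling them.

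**Working it through.** **1. Is it one analysis or two?** SAP 4.2.8 takes its model from 4.6.2, and both sections speak of testing. They therefore describe the same test with two missing-data rules.

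**2. What depends on it?** In the order of SAP 2.5.1, items 1, 2 and 6 are binary and items 3, 4, 5, 7, 8, 9 and 10 are continuous: 10 - 3 = 7. Item 3 (endoscopy subscore) stands before items 4 to 10, including binary item 6. The primary endpoint and the binary items count discontinuations as failures, so item 6 is affected only through the gate.

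**3. Closed-form illustration.** The plan has no figure here to reproduce. 75 per arm is the middle of the planned 70-80. The rest is assumed: SD of change 2.5, a linear course to Week 12, dropout (proportion d) spread evenly after Weeks 2, 4, 6, 8 and 10 and unrelated to outcome, SD unchanged by LOCF.

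The average last-observed fraction among dropouts is (2+4+6+8+10)/(5 × 12) = 0.5. So the LOCF mean is μ × (1 - d/2), where μ is the Week 12 mean. SE = 2.5 × √(2/75) = 0.408. One-sided rejection probability = Φ(-difference/SE - 1.96).

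- *No true difference, both arms -2.0.* Placebo 30%, active 10%: -2.0 × 0.95 + 2.0 × 0.85 = -0.20, rejection Φ(0.490 - 1.960) = 7.1%. Placebo 10%, active 30%: +0.20, rejection 0.7%. Equal dropout: 0 and 2.5%.
- *True difference -1.0 (placebo -1.0, active -2.0).* 20%/20%: -1.80 + 0.90 = -0.90. 30%/10%: -1.90 + 0.85 = -1.05. 10%/30%: -1.70 + 0.95 = -0.75.

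Under these assumptions MMRM without imputation targets 0 and -1.0 throughout. Take its SE as that of completers only; for -1.0 at 30%/10% or 10%/30% this is 2.5 × √(1/67.5 + 1/52.5) = 0.460. Its rejection probability is then 58%, against 73% (30/10) and 45% (10/30) for LOCF. At 20%/20% the two are about equal, 59% and 60%.

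**4. Dropout more likely in worse subjects.** This is a two-visit normal simulation with 70 per arm, SD 2 and true difference -1.30. It has 27 settings: correlation 0.4-0.8, dropout slope 0.5-1.5 per SD, and 40-80% of the change reached at the earlier visit. Dropout depends on the observed earlier score, so it is missing at random by construction, which favours MMRM. The test is a pooled two-sample comparison at Week 12.

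| Dropout placebo/active | Placebo change | LOCF estimate | LOCF null rejection |
|---|---|---|---|
| 20%/20% | 0 or -1.5 | -1.13 to -1.25 | 2.0-3.0% |
| 30%/10% | 0 | -1.24 to -1.42 | 3.0-6.7% |
| 30%/10% | -1.5 | -1.36 to -1.55 | 4.4-14.5% |
| 10%/30% | 0 | -0.93 to -1.20 | 0.7-2.3% |
| 10%/30% | -1.5 | -0.75 to -1.14 | 0.2-1.6% |

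The 14.5% is sensitive to the grid: other grids within the same ranges reached 12.7% and 12.9%. A likelihood analysis using the earlier visit gave -1.28 to -1.32.

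**5. The three endpoints measured once.** Endoscopy subscore, complete Mayo Score and IBDQ are scheduled after baseline only at Day 84 or Early Termination (Protocol Table 6-1; SAP Table 1). The Day 84 analysis window starts at Day 81, so an earlier termination value falls in an earlier window. No subject is scheduled to have both values, so the model has almost nothing within subject from which to inform a missing Week 12 value. In the step 4 simulation, completers only gave -0.97 to -1.24 with null rejection 0.1-1.9% (30/10), and -1.37 to -1.63 with 3.5-15.0% (10/30). Removing LOCF therefore does not settle these three. Under LOCF, a Full Analysis Set subject with no post-baseline endoscopy has only the baseline score to carry.

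**The case against.** The strongest reply is that the intended rule can be inferred. SAP 4.2.8 is the dedicated missing-data section and names the method for testing. The LOCF sentence in 4.6.2 repeats the protocol and looks like carry-over. That stands: a reader might infer that the SAP offers no clue which rule governs, and the documents do not support that. The sentence in 4.6.2 still has to go, because it sits in the testing paragraph without qualification.

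The rejection rates are also easy to over-read. They are per-test and ignore the gate: item 3 is reached only after the primary and items 1 and 2 succeed. With no true effect on any endpoint, 30/10 dropout, placebo improving, and assumed responder cuts at the best 27% (item 2) and best 10% (remission), items 2 and 3 were both rejected in 2.0-4.8% of trials. Requiring the remission-like test as well gave 0.4-1.6%. The rates also come from a pooled two-sample test. The primary method works stage by stage, with Stage 1 at about 15-20 per arm (60-80 over four arms). No document supports a threefold dropout imbalance. All of this stands, so the figures show direction and sensitivity. They are not a type 1 error estimate for the trial.

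A reader might infer that the SAP is silent on whether an Early Termination value enters the model. Read together, 4.2.8 (data from all visits analysed jointly) and 4.2.9 (windows by study day) place it there, at its own window. What remains is the lack of any paired Week 12 value.

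A reader might also infer that SAP 4.2.1 confines formal testing to the primary endpoint. It names that endpoint but does not exclude others, so its tension with 4.2.5 is by implication. The exploratory label in 4.6.2 can be read as covering only the pooled estimates, but the SAP does not say so.

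**Conclusion.** The contradiction between SAP 4.2.8 and 4.6.2 is established from the text and needs no assumption. It concerns seven of ten hierarchical endpoints directly and item 6 through the gate. It should be fixed, but it does not threaten the primary analysis.

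Its size is illustrative. With equal dropout, LOCF keeps null rejection near 2.5% and somewhat attenuates a true effect. With unequal dropout it errs in favour of the arm that loses fewer subjects. This rests on assumed SDs, dropout rates and time courses, and MMRM is on target only where dropout is missing at random.

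A reader might infer that SAP Section 5 was wrong when written. That is not shown. The statement is made as of the SAP's own date, and the SAP schedule differs from the current protocol (screening from Day -35 against Day -42; at least 3 minutes' rest against 5), so the SAP appears to follow an earlier protocol version. Only a mismatch with the current Protocol 7.4 is demonstrated.

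**What to change.** Before unblinding, in the SAP:

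1. Delete the LOCF sentence from 4.6.2, so that the no-imputation MMRM of 4.2.8 is the tested analysis. Keep LOCF as a sensitivity analysis.
2. For endoscopy subscore, complete Mayo Score and IBDQ, name one rule for subjects without a Week 12 value, including how an Early Termination value is used, with the alternative as a sensitivity analysis. No particular imputation model is prescribed here. For example, simulated imputation of Week 12 from earlier symptom scores gave -1.28 to -1.32 (truth -1.30) when dropout followed those scores. When dropout followed the endpoint itself, it gave -1.02 to -1.28 (30/10) and -1.32 to -1.58 (10/30).
3. If that is the intent, state in 4.6.2, consistently with 4.2.5 and 4.2.1, that these endpoints are tested in the hierarchy with p-values derived as for the primary endpoint, and that the exploratory label covers only the pooled estimates.
4. Record in Section 5 the differences from the current Protocol 7.4: no LOCF in the tested model, and an added hierarchy. SAP 1.2 already undertakes to outline such differences.

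The cost is wording in SAP 4.2.1, 4.2.5, 4.2.8, 4.6.2 and Section 5, plus programming of the rule chosen under item 2. No new data are needed.

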where  $SE(\hat{\delta}_2) = \sqrt{\frac{\pi_t(1-\pi_t)}{n_{2t}} + \frac{\pi_c(1-\pi_c)}{n_{2c}}}$  and  $n_{2t}, n_{2c}$  are the number of subjects for the active dose and placebo group at the second stage respectively. Since we don't know  $\delta, \pi_t, \pi_c$ , we will replace them by those observed from the first stage data in the conditional power calculation.

PD, efficacy, and safety data will be analyzed to model dose- and exposure-response from Stage 1 of the trial to allow dropping of an ineffective or redundant arm(s). It is also possible that a new dose arm (not tested in Stage 1 of the trial) could be added in Stage 2 for exploratory purposes. Since the trial provides for a 12-week treatment period, it is expected that an additional approximately 60 subjects would be randomized in equal proportions to the 4 treatment groups while the first approximately 60-80 subjects' 12-week data are accumulated and analyzed. Hence, in Stage 2 the remaining subjects would be randomized in equal proportions to the selected dose(s) and placebo. This would yield approximately 70-80 subjects per treatment group for the selected doses. The final analysis will combine all observed data from both Stages 1 and 2.

Dose selection will further be made in consideration of safety data and sound clinical judgment, and will be made by the ADRC), which will be comprised of the DMC and a representative of the Sponsor (not involved in the direct conduct of the study). No pre-specified algorithm will be defined for the IA. Only the ADRC, which will make the dose selection for Stage 2, and the Independent Statistical Center, which will perform the IA, will be unblinded.

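### SAP 4.6.2 gives two incompatible p-value rules for the seven continuous secondary endpoints in the one-sided 0.025 hierarchy, and one of them leaves interim dose selection uncorrected

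*SAP*

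**What the plan says.** SAP 4.2.5 sets up the secondary testing: "Testing of secondary endpoints will only be performed if the primary efficacy null hypothesis is rejected"; then "A hierarchical testing procedure will be used for the multiple secondary endpoints at the 0.025 (one-sided) alpha level"; and "The first ten secondary endpoints will be tested in the order that they are presented in Section 2.5.1". Only Week 12 counts for endpoints measured repeatedly. In the SAP 2.5.1 list, items 1, 2 and 6 are binary. Items 3, 4, 5, 7, 8, 9 and 10 are continuous: the endoscopy, rectal bleeding and stool frequency subscores, complete and partial Mayo, calprotectin and IBDQ.

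For those seven, one paragraph of SAP 4.6.2 says three things:

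- "Hypothesis testing for all continuous secondary endpoints will be conducted using repeated measures mixed analysis of covariance model"
- "These analyses will be based on the Stage 1 and Stage 2 combined data for exploratory purposes"
- pairwise comparisons with placebo have "p-values derived as described in the analysis of the primary efficacy endpoint"

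SAP 4.2.8 says of the mixed model, without mentioning stages: "This method will be used in the testing of the secondary endpoints".

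On dose selection, SAP 4.3 says: "PD, efficacy, and safety data will be analyzed to model dose- and exposure-response from Stage 1 of the trial to allow dropping". It fixes no selection algorithm. Protocol 7.4 has the same pooled, exploratory sentence but no secondary hierarchy. SAP Section 5 nevertheless declares no change from the protocol.

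**The concern.** The paragraph assigns two tests, and two statuses, to the same seven endpoints. Read one way, the test is a single contrast from a model fitted to everyone, labelled exploratory. Read the other way, it is the adaptive combination test built for the primary.

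The choice matters because the retained doses are picked by an unblinded committee that has seen Stage 1 efficacy data. A dose that looks good by chance in Stage 1 is more likely to be kept. A pooled contrast then counts that chance excess again at an unadjusted 0.025. The combination test is the plan's device for dealing with this.

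For a borderline result, the claim depends on which sentence the programmer follows, and so does every later step. Endoscopic remission (item 6, binary) can be reached only through continuous items 3 to 5.

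**Working it through.** **The two rules side by side**

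| | Pooled rule (SAP 4.6.2, 4.2.8) | Stage-wise rule (SAP 4.6.2 referring to 4.6.1) |
|---|---|---|
| Data | both stages in one model | a p-value from each stage |
| Stage 1 adjustment | none | min{3p(1), 1.5p(2), p(3)} |
| Combination | none | Φ(w1Φ⁻¹(p̃1) + w2Φ⁻¹(p2)), w1 = √t1, w2 = √(1−t1) |
| Status | exploratory | hierarchical, one-sided 0.025 |

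SAP 4.6.1 defines its stage p-values for differences of proportions and gives no number for t1. Nothing tells the programmer to fit the mixed model by stage.

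**The plan's own figures.** The documents give no secondary error rate beyond the nominal 0.025. SAP Table 2 covers the primary. At N=240, with two doses kept, 60 subjects in Stage 1 and no separate overrun, simulation gives 90.3%, 81.1% and 1.7% against the stated 91%, 82% and 2.2%. Power agrees within 2 points. The null figure is about one standard error away (√(0.022×0.978/1000) ≈ 0.5 points). With the 60-subject overrun spread over four arms, power is 88.5% and 78.1%, short of Table 2; that is a separate matter.

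**Inputs**

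- Stage 1: 60–80 subjects over four arms, so n1 = 15–20 per arm (SAP 2.1).
- Final size: 70–80 per selected arm (SAP 2.1). With one dose kept and about 210 in total: 15 + 15 + (210−120)/2 = 75, or 20 + 15 + (210−140)/2 = 70.
- Stage 1 share f = n1/n: from 15/80 = 0.19 to 20/70 = 0.29.
- Assumed: one dose kept as best of three; a correlation ρ between the selection score and the endpoint; the endpoint null at every dose; a z test on Week 12 change standing in for the mixed model.

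**Error of the pooled test.** The pooled statistic is √f·Z1 + √(1−f)·Z2. The expected maximum of three standard normals is 3/(2√π) = 0.846, with variance 0.559. Dividing by √2 for the comparison with placebo, the selected dose's Z1 has mean 0.846ρ/√2 = 0.598ρ and variance 1 − 0.220ρ². Approximately:

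error = 1 − Φ[(1.96 − 0.598ρ√f) / √(1 − 0.220fρ²)]

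Example, f = 20/70, ρ = 1: shift 0.320, SD 0.968, (1.96 − 0.320)/0.968 = 1.694, error 4.5%.

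| ρ | f = 15/80 | f = 15/75 | f = 20/70 | Simulation |
|---|---|---|---|---|
| 0 | 2.5% | 2.5% | 2.5% | 2.5% |
| 0.3 | 3.0% | 3.0% | 3.1% | 3.0–3.1% |
| 0.5 | 3.3% | 3.3% | 3.5% | 3.3–3.5% |
| 0.7 | 3.6% | 3.7% | 3.9% | 3.6–3.9% |
| 1.0 | 4.1% | 4.2% | 4.5% | 4.1–4.5% |

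**Requiring the primary to be rejected first**, selecting one dose on observed binary remission:

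| True remission rates (placebo, 150, 300, 900 mg) | Pooled-test error |
|---|---|
| 0.10, 0.31, 0.31, 0.31 | 2.9–4.1% |
| the two SAP Table 2 dose-response scenarios | 2.4–3.8% |
| 0.10 in all arms | 0.2–0.6% |

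**Two doses kept.** The average per selected dose is 2.7–3.3% for ρ from 0.3 to 1.0.

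**Stage-wise rule.** On the same assumptions the error is about 1.6–2.3%. The lower values come from the full closed test, the higher from the single Simes formula printed in SAP 4.6.1.

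**Disagreement.** With an assumed true effect of 0.3–0.5 SD, the two rules reach different decisions in about 4–12% of trials.

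**The case against.** The strongest reply is that the paragraph already contains the correction. If its p-value sentence governs, the test is stage-wise and there is no inflation. Reference to combined data need not mean an uncorrected test: Protocol 7.4 and SAP 2.1 use similar language around the primary, whose test is plainly stage-wise. One can read the pooled model as supplying estimates and the primary's method as supplying p-values. That reading is available, but the SAP neither states it nor makes it executable. The pooled sentence directly follows the one on hypothesis testing.

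The second reply concerns size, and most of it stands. Selection also weighs safety, PD and redundancy of arms, so strict best-of-three is near the worst case. Keeping one dose is the 210-subject alternative. No continuous endpoint is tested until clinical and endoscopic response have also been rejected, and further preconditions can only lower the rates. Five of the seven endpoints are components of remission or sums containing them, so an exact null alongside a real remission effect is hard to construct. Calprotectin and IBDQ are the more plausible nulls, and they come last.

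Third, SAP 4.2.1 reserves formal testing for the primary and Protocol 7.4 calls these analyses exploratory. That lowers the stakes, but it contradicts SAP 4.2.5 and so adds to what must be reconciled.

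**Conclusion.** The contradiction is established by the text alone: two p-value rules, and an exploratory label on endpoints in an alpha-controlled hierarchy. It should be resolved before unblinding.

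The numerical consequence is conditional. About 3.0–4.5% applies to the selected dose only under the pooled rule, with one dose kept as best of three, a correlation of 0.3–1.0, a true null for that endpoint, and the primary and earlier steps rejected. The top of that range needs selection on the endpoint itself; selection on binary remission gives at most about 4.1%.

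A reader might infer more than this in three ways:

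- **That the secondary error rate simply is 3.0–4.5%.** The documents give neither a correlation nor a selection rule, and one of the two sentences produces no inflation.
- **That selection drives the 4.9–5.9% chance of at least one false claim when two doses are kept.** That figure is already 4.5% at zero correlation, so it mostly reflects testing two doses.
- **That the primary is compromised.** Its combination test is specified separately and is not touched by this paragraph.

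**What to change.** In SAP 4.6.2, make one rule govern the hierarchical Week 12 test of each continuous endpoint:

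1. Fit the mixed model separately in Stage 1 and Stage 2 subjects.
2. Take the one-sided dose-versus-placebo p-value at Week 12 from each stage.
3. Combine them with the primary's Simes adjustment and inverse-normal weights, with a numerical t1 fixed in advance.
4. Keep the model on both stages together for estimates, confidence intervals and plots, labelled exploratory, and move the pooled-data sentence there. Align SAP 4.2.8.
5. State how two retained doses share alpha.

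If the sponsor means these endpoints to be exploratory, as Protocol 7.4 says, the alternative is to remove all seven from the SAP 4.2.5 hierarchy and report their p-values as descriptive. Either way, SAP Section 5 should record the departure from, or agreement with, the protocol.

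The cost is wording plus one extra model fit per endpoint and stage, with no new data or patients. Against the uncorrected pooled test, the stage-wise rule gives up roughly 2–12 points of nominal power in most settings with assumed effects of 0.3–0.5 SD, and less than 1 point at 0.5 SD with correlation 0.3. Part of that loss is the inflation being removed.
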